1.20 Screening

1.20.1 Screening Assessment

In combination with evaluation of eligibility criteria mentioned above, eligibility of OUD or non-medical use of opioids will be determined using the screening assessment outlined below. During the screening assessment, visitors and family will be asked to leave the room and the remainder of the consent process and interview will occur without visitors except for when the patient specifically requests that their visitor be allowed to stay. The screening assessment will not be required for patients who are being treated for OUD overdose. To avoid interrupting patient care, the logistics of conducting screening in a medical setting require that the screening process be relatively brief. During defined recruitment hours, research staff assigned to the study will screen ED patients who are possibly eligible for the study. Depending on the patient flow, patients will be approached either prior to or after the evaluation by a clinician.

Research staff will approach patients consecutively and ask them if they are willing to participate in anonymous screening for participation in a health study. Participants will provide verbal (not signed) consent for the anonymous collection of screening data, using a brief IRB-approved script. For each day of screening, the number of patient refusals and other reasons for patient inability to participate will be recorded on the Screening Log to determine whether they met inclusion criteria (and if not, why). The RA will document the screening and eligibility status of all individuals approached on the Screening Log. Screening efforts will continue until recruitment hours have ended.

All participants reporting any opioid use during screening will receive a brochure on overdose prevention and a Project ASSERT brochure, which includes information on local treatment resources and contact information of hospital staff that specialize in referrals to treatment.

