1.8 Primary Objective

The primary objective is feasibility testing to determine the proportion of ED patients with OUD, non-medical opioid use or overdose who are willing to share electronic health data with researchers and complete PROs delivered by a mobile-based technology platform. We hypothesize that patients will be willing to enroll and provide PROs both during and after discharge. The primary objective will be measured by the proportion of people who qualify for study criteria and enroll in the study by signing up for Hugo and sharing their EHR with researchers for this study, as well as response rates to electronic surveys and lost-to-follow-up (LTFU) rates among those who enroll. If successful, electronic PROs could offer an opportunity to improve follow-up and treatment among patients with OUD after discharge from the ED.

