1.13 Primary Outcome Measures

The primary outcome measures are the proportion of people who qualify for study criteria and enroll in the study, as well as response and follow-up rates among those who enroll.

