1.17 Participant Inclusion Criteria

Individuals must meet all of the following inclusion criteria in order to be eligible to participate in the study:

- Adult patient presenting to the YNHH YSC or SRC EDs
- History of opioid use disorder or non-medical use of opioids, as measured by screening assessment OR receiving treatment for opioid overdose
- Willingness and ability to complete electronic surveys via a smartphone or computer

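### The primary enrollment proportion has no rule for patients who refuse the voluntary opioid screen; leaving out those who would have qualified can only raise it

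*Protocol*

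**What the plan says.** Protocol section 1.8 sets the primary objective as the proportion of ED patients with OUD, non-medical opioid use or overdose who are willing to share data and complete electronic surveys. Section 1.13 turns this into a measure: "The primary outcome measures are the proportion of people who qualify for study criteria and enroll in the study". Response and follow-up rates among enrollees are listed after it. The Statistical Design and Analyses section repeats the same definition.

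The opioid criterion in section 1.17 is: "History of opioid use disorder or non-medical use of opioids, as measured by screening assessment OR receiving treatment for opioid overdose". Section 1.20.1 confirms that "eligibility of OUD or non-medical use of opioids will be determined using the screening assessment outlined below". The same section makes the assessment voluntary: "Research staff will approach patients consecutively and ask them if they are willing to participate in anonymous screening for participation in a health study". Verbal consent is taken for it, and the data are anonymous. For overdose, "The screening assessment will not be required for patients who are being treated for OUD overdose".

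Two further provisions bear on the point. Section 1.20.1 has refusals recorded daily on the Screening Log and asks the research associate to document screening and eligibility status for all individuals approached. Section 1.19 describes an EHR review and a question to the treating clinician before approach, for patients found on the ED trackboard. It describes no such check for patients referred by staff.

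**The concern.** The outcome is willingness, measured by enrollment. On the OUD and non-medical-use route, a first act of willingness (agreeing to be screened) comes before the step that establishes whether the patient belongs in the denominator. Two patients with OUD who both end up not enrolled can therefore be treated differently. One who answers the screen, qualifies and then declines is plainly a non-enrolled qualifier. One who declines at the screening question has no screen result, and the protocol does not say whether that patient counts.

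Refusal at first contact may well be where the least willing patients are found. If they leave the denominator, the study's headline feasibility figure describes people who had already agreed to something. Anyone planning a later ED study from it would expect more enrollees per eligible patient approached than they would get.

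**Working it through.** **The plan's own figures.** The protocol states no enrollment proportion, refusal rate or target rate, so there is none to reproduce. The only related number is about 200 enrollees, chosen for feasibility (section 1.3). The schedule in section 1.4 agrees with it: 10 + 190 = 200.

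**Status of each kind of patient under the text.**
- Screened, qualifies, declines the study: in the denominator, not in the numerator.
- Refuses the screen, not an overdose patient: no result on the assessment that measures the opioid criterion. A status must be logged, but no method of determining it is given.
- Overdose patient who refuses at first approach: meets the opioid criterion without the screen. However, section 1.17 requires all criteria, including willingness and ability to complete electronic surveys. The question on smartphone or computer access sits on the Quick Screen Form (Study Assessments), which is described for patients being screened for OUD or non-medical use. This status is not settled either.

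**Direction.** Let E be the number enrolled, Q the number known to qualify, R the number of screen refusers with unknown eligibility, and π the share of R who would have qualified.
- Rate with refusers left out: E/Q.
- Rate with eligible refusers included: E/(Q + πR).

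Refusers add nothing to E, so E/Q ≥ E/(Q + πR). The two are equal only if R = 0 or π = 0.

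**Size, by assumption.** E = 200 is the planned enrollment; Q, R and π are assumed.

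| Q | E/Q (Wilson 95% CI) | R | π = 0.25 | π = 0.5 | π = 1 |
|---|---|---|---|---|---|
| 250 | 80.0% (74.6 to 84.5) | 50 | 200/262.5 = 76.2% | 200/275 = 72.7% | 200/300 = 66.7% |
| 250 | 80.0% | 100 | 200/275 = 72.7% | 200/300 = 66.7% | 200/350 = 57.1% |
| 400 | 50.0% (45.1 to 54.9) | 50 | 200/412.5 = 48.5% | 200/425 = 47.1% | 200/450 = 44.4% |
| 400 | 50.0% | 100 | 200/425 = 47.1% | 200/450 = 44.4% | 200/500 = 40.0% |

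The difference runs from 3.8 to 22.9 points at Q = 250 and from 1.5 to 10.0 points at Q = 400. In several of these cells the corrected rate lies below the confidence interval of the uncorrected one, so the sampling interval would not convey the uncertainty.

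**Screened route against pooled rate.** If a share r of screened-route patients refuse, and refusers are eligible as often as those screened, the rate on that route is inflated by 1/(1 − r): 11% relative at r = 10%, 25% at 20%, 43% at 30%. The primary measure pools in overdose patients, who need no screen. If they form a share s of eligible patients and none is lost to a screen refusal, the pooled factor is 1/(1 − (1 − s)r). With s = 0.5 (assumed; the protocol gives no share) this is 1/0.90, or 11%, at r = 20%, and 1/0.85, or 18%, at r = 30%.

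**The case against.** The strongest reply is that no sentence in the protocol removes screen refusers from the denominator. Section 1.20.1 requires an eligibility status for everyone approached, and section 1.19 gives trackboard patients an EHR and clinician check first. This stands as far as it goes: it is too strong to say that refusers never receive a qualifying status. But the check yields only apparent eligibility, for one of two identification routes, while section 1.17 ties the criterion to the screening assessment. Requiring a status does not supply a means of finding it.

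A reader might also infer that overdose refusers stay in the denominator while OUD refusers drop out, so that the two entry routes are not comparable. The documents do not support this. An overdose patient who refuses at first contact has not been shown to meet the willingness and device criterion, and may equally be classed as not qualifying. No comparison by route is planned in any case. Nor can 1/(1 − r) be read as the inflation of the primary measure, since it applies to the screened route alone.

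Two further points have weight. Declining anonymous screening for a health study is not the same as declining to share records through Hugo, so an estimate that assumes refusers resemble those screened should not become the headline. And this is an exploratory pilot on a convenience sample, with no target rate or decision threshold resting on the figure.

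It may be said that unknown eligibility is a matter for the statistical analysis plan. The denominator, however, is fixed in the protocol, and what is logged at refusal is a protocol procedure. Because screening data are anonymous, a later plan may be unable to recover which refusals came before screening unless they were tallied at the time.

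**Conclusion.** The point holds in a limited form. The primary enrollment proportion is defined among people who qualify, qualifying on the OUD and non-medical-use route depends on a voluntary screen, and patients who refuse it have no stated way to be classed and no counting rule. If would-be-eligible refusers are left out, the bias can only be upward.

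The amount cannot be obtained from the document. It is zero if no refuser would have qualified. Under the assumed scenarios above it is 1.5 to 22.9 percentage points, and in the pooled rate it is smaller than the screened-route factor. It would be going too far to say that the rate will be overstated, since that depends on how the log is completed and on who refuses. The matter is worth settling before enrollment because this is the first-listed primary measure of a feasibility study; it does not threaten the conduct of the study.

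**What to change.** In sections 1.8 and 1.13 and in Statistical Design and Analyses:
- Keep enrolled over known-qualifying, E/Q, as one reported figure.
- Report with it the bounds that count none and all of the unknown-eligibility refusers as eligible, E/Q and E/(Q + R). The first equals the figure above.
- Give a proportional estimate, E/(Q + eR), as a sensitivity analysis only, with e the eligible fraction among those screened on the same identification route.

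On the Screening Log, tally patients who refused before screening separately from those who qualified and then declined the study. Split both by identification route (trackboard or referral) and by whether the patient was being treated for overdose.

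For example, suppose 500 patients are approached for screening, 100 refuse, 320 of the 400 screened qualify, and 200 enroll (all assumed, and all on the screened route). The report would read 200/320 = 62.5%, with lower bound 200/420 = 47.6%. With e = 320/400 = 0.8, the sensitivity estimate is 200/(320 + 80) = 50.0%.

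The cost is a short addition to the outcome definition and extra tallies on a log that already records refusals, with no new patients or procedures. The drawback is that the headline rate becomes a range, and its lower bound may be unflattering.

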1.2 Study Design and Outcomes

This is a single-center observational study that will be conducted in the Yale-New Haven Hospital (YNHH) York Street Campus (YSC) and Saint Raphael Campus (SRC) Emergency Departments (ED)s using a convenience sample. It is an exploratory pilot project designed to inform and enhance the use of EHR data and PROs to conduct opioid-related research in the ED.

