The Hugo platform has been used across a range of studies to engage populations of varying backgrounds and currently has more than 1,000 users. The age range in prior studies generally ranged from 20 to 80 years, suggesting an acceptability across ages. Hugo is currently in use by several industry, foundation and FDA sponsored studies. With respect to reach, in a study funded by the Aetna Foundation, in partnership with Project Access New Haven, Hugo was used to understand its acceptability to lower health literacy populations. The results showed that this group were avid adopters of the technology, reported being empowered by being given agency over their data, and participated with high response rates (>80%), which were similar for the Spanish version of the platform. Overall, projects using Hugo have typically had ePRO response rates as high as 70% on initial delivery of survey questions. When automated reminders were sent to study participants who did not initially respond, response rates increased further to 80% and above. In some studies response rates through mobile delivery have reached 90% and higher.

Several studies involving Hugo validated the EHR data from Hugo with EHR data collected through traditional methods. As an example, one industry-sponsored project found a 100% match between patient demographic and medical history and event data captured through Hugo and data collected from manual abstraction from the EHR. Importantly, Hugo enabled the capture of events almost immediately after they occurred.

*Note that the statistics referenced above are not currently published in peer-reviewed journals but are private data provided by Hugo, based on their experience and internal evaluation of their platform.

Site Selection:

Yale New Haven Health (YNHH) provides health care to children and adults living in the southern portion of Connecticut, from the New York border to Westerly, Rhode Island. The Yale New Haven Health Emergency Departments at the York Street and Saint Raphael locations provide service to the Greater Bridgeport, New Haven and New London catchment areas. In 2016, 240,000 (19%) individuals within this catchment area received emergency or primary care from YNHHS. Of these, 8,503 unique patients had a diagnosis of alcohol use (AUD) and 1,020 of opioid use disorder (OUD). Forty-three percent of the more than 9,000 SUD patients identified in our EDs were seen two or more times in that year.

Study Rationale:

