1.19 Strategies for Recruitment and Retention

Identification:

Participants will be identified in multiple ways, including:

- Electronic trackboard: The RA will continually monitor the ED trackboard for patients with a chief complaint of overdose or intoxication and conduct a brief EHR review for patients with these relevant chief complaints to assess inclusion/exclusion criteria. For patients that appear eligible, the RA will ask the treating ED clinician if the patient is currently clinically sober and meets inclusion and exclusion criteria to the best of the ED clinician's knowledge. The RA will then approach any patients that remain eligible. If a patient appears eligible but is currently intoxicated, he or she will be approached once the clinician deems them sober enough to have the capacity to consent to research.
- Referrals: All ED staff will be informed of our study and asked to refer patients when appropriate. Staff includes physicians, nurses, technicians and Project ASSERT staff. Project ASSERT is a YNHH ED service provided by health promotion advocates that connects patients with substance use disorders to treatment. ED staff will alert the RA of potential patients in person, by phone, email or Epic inbox.

Special Cases: It is possible that eligible patients screened in the ED may be admitted, in which case they will be followed to the inpatient floor if necessary to complete enrollment. Patients who are approached by research staff to participate, but decline participation, will not be re-approached during hospitalization, even if they were clinically intoxicated at the time they declined participation. It is also possible that participants enrolled in the ED could be on parole, which by definition qualifies as a prisoner in the state of Connecticut. For this reason, we will obtain OHRP Prisoner Certification to include individuals defined as prisoners by the state or federal regulations, which will be obtained prior to beginning enrollment. We do not plan to follow participants if incarcerated, however, as surveys are electronic and it is highly unlikely that prisoners would have access to a smartphone or computer while incarcerated. We will also not ask any questions at baseline or follow-up regarding parole or incarceration, given OHRP approval to include such participants.

Retention:

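### As written, anonymous screening with no rule for repeat approaches does not secure a person-level denominator for the primary enrollment proportion

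*Protocol*

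**What the plan says.** Protocol section 1.13 sets the unit of the primary outcome: "The primary outcome measures are the proportion of people who qualify for study criteria and enroll in the study". Section 1.8 and the statistical section repeat it.

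The denominator comes from screening. Section 1.20.1 says: "Participants will provide verbal (not signed) consent for the anonymous collection of screening data". It then sets the counting rule: "For each day of screening, the number of patient refusals and other reasons for patient inability to participate will be recorded on the Screening Log". The same section has the research assistant log the screening and eligibility status of every individual approached.

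On returning patients, section 1.19 says only that those who "decline participation, will not be re-approached during hospitalization". It gives no rule for a later ED visit. Section 1.7 describes patients with opioid use disorder (OUD) as at risk of high ED use and, under site selection, reports: "Forty-three percent of the more than 9,000 SUD patients identified in our EDs were seen two or more times in that year".

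On how patients are found, section 1.2 describes a study "using a convenience sample". Section 1.20.1 says "Research staff will approach patients consecutively". Section 1.19 describes two routes: trackboard monitoring for overdose or intoxication complaints, and discretionary referral by ED staff.

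**The concern.** A proportion of people needs each person counted once. Enrollees can be identified, but decliners cannot. If the same person declines at two visits, two anonymous entries look like two people. The denominator grows while the numerator does not, so willingness to take part is understated.

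Enrollment runs from 15 April to 31 October 2019 (section 1.4), about six and a half months, at two EDs, so a decliner has time to return. The loss happens at the bedside. Once decliners are logged without a repeat marker, nothing in the dataset can link their entries, and an analysis plan cannot put that right afterwards.

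The sampling frame raises a lesser issue. Patients flagged on the trackboard and patients chosen by staff for referral may enroll at different rates, and the protocol does not say that the route is recorded.

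**Working it through.** The protocol gives no expected enrollment proportion and no precision target, so there is no stated figure to reproduce. The sample size of about 200 rests on feasibility (section 1.3), and its breakdown agrees: 10 + 190 = 200 (section 1.4).

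**Inputs**
- Enrolled: 200 (section 1.3).
- True person-level proportion p: not in the protocol; assumed 0.30, 0.50 and 0.70.
- Share r of decliners logged once more as eligible and declining: not in the protocol; assumed 0.10, 0.20 and 0.43. The last borrows the section 1.7 figure as a stress value.

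**Formulas**
- Eligible persons: N = 200/p.
- Logged proportion: 200 / (N + r × (N − 200)).

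**Worked case, p = 0.50.** N = 400, with 200 decliners. The Wilson 95% interval is 0.451 to 0.549, a half-width of (0.549 − 0.451)/2 = 0.049.
- r = 0.10: 200/(400 + 20) = 200/420 = 0.476, a shift of 2.4 points.
- r = 0.20: 200/(400 + 40) = 200/440 = 0.455, a shift of 4.5 points.
- r = 0.43: 200/(400 + 86) = 200/486 = 0.412, a shift of 8.8 points.

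**All assumed values** (N rounded to whole persons)

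| p | N | Wilson 95% interval | r = 0.10 | r = 0.20 | r = 0.43 |
|---|---|---|---|---|---|
| 0.30 | 667 | 0.266 to 0.336 | 0.280 | 0.263 | 0.230 |
| 0.50 | 400 | 0.451 to 0.549 | 0.476 | 0.455 | 0.412 |
| 0.70 | 286 | 0.644 to 0.750 | 0.679 | 0.660 | 0.619 |

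At r = 0 the log returns p (0.699 in the last row, from rounding N).

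**What the 43% measures.** The section 1.7 counts are 8,503 alcohol and 1,020 opioid diagnoses, 9,523 in all. The opioid share is 1,020/9,523 = 10.7%, so about 89% are alcohol diagnoses. The figure covers a full year and all visits. It is not a rate of re-approach among people with OUD during enrollment.

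**If some repeat decliners enroll.** Suppose a share c of those re-approached now enroll. With p = 0.50, the logged proportion is (200 + c × r × 200)/(400 + r × 200). At c = 0.40 (assumed):
- r = 0.20: (200 + 16)/(400 + 40) = 216/440 = 0.491.
- r = 0.43: (200 + 34.4)/(400 + 86) = 234.4/486 = 0.482.

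Against a first-approach proportion of 0.500, the error is then only 1 to 2 points.

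**The case against.** The strongest reply is that the text does not force double counting. The log covers every individual approached, only refusals and reasons for non-participation are tallied by day, and trackboard patients have their records reviewed before approach. This stands against saying that the log cannot give a person-level count, or that it is kept by visit. A reader might infer either, but the protocol states neither. It does not remove the gap: no step records an earlier approach, and the record review covers the trackboard route only.

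A reader might also infer that the same person could enroll twice unnoticed, because the exclusions in section 1.18 do not mention prior enrollment. The protocol does not support this. Enrollees sign consent and hold a named Hugo account linked to the study (section 1.22), and their medical record number is extracted (Study Assessments). Section 1.24 also bars re-enrollment after withdrawal, which presupposes that identity is known.

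The magnitude is open to fair attack. Every repeat rate is assumed. At 10% the shift stays inside the sampling interval in all three cases. The illustration treats every repeat refusal as an eligible person, although someone who refuses screening may never have eligibility established. A gap of 5 to 10 points under 40% conversion can be produced by comparing the log with the proportion ever enrolled: with p = 0.50, 216/400 = 54.0% against 49.1%, and 234.4/400 = 58.6% against 48.2%. That gap comes from switching the target away from first approach.

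On sampling, approaching patients in sequence during set recruitment hours can fit a convenience sample. Referral affects who is selected, not whether a person is counted once, and nothing in the protocol shows that referred patients are more cooperative.

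Finally, this is an exploratory pilot with no success threshold, and counting rules often sit in an analysis plan or log form not shown here. But a counting rule cannot be applied to decliners whose repeat status was never captured.

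**Conclusion.** The concern holds in limited form. The protocol defines its primary enrollment proportion on people, but it does not secure a denominator in which each decliner is counted once. For people who decline more than once, the bias is downward and cannot be repaired after data collection.

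Its size is unknown. With a true 50% and no conversion at the second approach, re-logging 20% of decliners moves the estimate by nearly the full 95% half-width (4.5 against 4.9 points). At 10% the shift is 2.4 points. The 8.8 points at 43% is a stress case and should not be read as an expected error. Conversions at re-approach shrink the error against a first-approach target.

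The wording on consecutive approach, referral and convenience sampling leaves the sampling frame unclear. That is a secondary point about description and generalizability. The change is worth making before screening starts, because the enrollment proportion is a primary outcome and the remedy is small.

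**What to change.** - Add one item to the Screening Log: previously approached for this study (yes/no/unknown). Complete it for every individual approached, including overdose patients and those who refuse screening. Placing it only on the Quick Screen Form would miss both groups.
- In section 1.13, define the primary denominator as unique eligible persons at first approach, and report repeat approaches separately.
- Record the identification route (trackboard or referral) and report the enrollment proportion by route descriptively. The trackboard route should not become the primary analysis: it is limited to overdose and intoxication complaints, is itself filtered by the treating clinician, and would move away from the stated population.
- Align sections 1.2, 1.19 and 1.20.1 so that they describe one sampling method.

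The cost is two tick-boxes and a few sentences. Screening stays anonymous and clinical care does not change. The drawback is reliance on the patient's or research assistant's recall of an earlier approach, so the number of unknown answers should be reported.
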